7.3. Stopping and Discontinuation Criteria

7.3.1. Discontinuation Criteria related to the Study

- Insufficient recruitment of less than 30% of the total patient sample in one year
- If reasonable suspicion exists that any serious and life-threatening side effects occur significantly more frequently than usual in patients with the inclusion diagnosis, the study will be discontinued.

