4. STUDY OBJECTIVES

The study shall assess the therapeutic effect and the safety of a single daily dose of 90 mg of N-Pep-12 in supporting neurorecovery in comparison to a control group of patients after stroke. This is an exploratory study, and the dosage, route of administration and intervention duration were chosen according the current instructions for use provided by the manufacturer of N-Pep-12. The study aims to show the superiority of N-Pep-12 over the control group in the neurorecovery outcome after 360 days.

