7.4. Randomization, Blinding and Unblinding

8. PATIENTS WHO MEET THE INCLUSION AND EXCLUSION CRITERIA WILL BE RANDOMLY ASSIGNED TO THE TREATMENT GROUP OR CONTROL GROUP, IN A 2:1 RATIO. PATIENTS IN THE TREATMENT GROUP WILL RECEIVE ACTIVE DIET SUPPLEMENTATION MEANWHILE, THE PATIENTS IN THE CONTROL GROUP WILL NOT RECEIVE ANY KIND OF MEDICATION OR PLACEBO. INVESTIGATIONAL PRODUCTS

The regular marketable merchandise of N-Pep-12 (Cebrium) capsules will be obtained from pharmaceutical wholesalers in Romania.

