11.3. Serious Adverse Event or Serious Adverse Reaction (SAE/SAR)

An adverse drug reaction is considered SERIOUS if it:

- Results in death
- Is life threatening

- Requires additional inpatient hospitalization or prolongation of existing hospitalization
- Results in persistent or significant disability / incapacity
- Results in a congenital anomaly or birth defect
- Other medically significant event that requires immediate medical or surgical intervention

An adverse drug reaction is considered UNEXPECTED if it:

Is not consistent with the Investigators' Brochure or SPC

CAUSAL RELATIONSHIP means:

- There are facts/evidence to suggest a causal relationship
- As judged by the reporting health care professional to have a reasonably suspected causal relationship

Expedited Reporting is required if all of the following criteria apply (ICH E2A):

- Serious
- Unexpected
- Causal relationship to study treatment

NOTE

Death: is the outcome of an adverse event. The event to be reported comprehensively is the medical condition leading to death, e.g., underlying disease or accident.

Life-threatening: in the definition of a serious adverse event or adverse reaction, "life-threatening" refers to an event in which the patient was at risk of death at the time of the event; it does not refer to an event that hypothetically might have caused death if it was more severe.

Medical judgment should be exercised in deciding whether an adverse event/reaction is serious in other situations. Important adverse events/reactions that are not immediately life-threatening or do not result in death or hospitalization but may jeopardize the patient or may require intervention to prevent one of the other outcomes listed in the definition above should also be considered serious.

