11.7. Reporting of Serious Adverse Events

All serious adverse reactions and all unexpected serious adverse reactions with at least a suspicion of a causal relationship to the investigational product must be reported to the manufacturer within 24 hours (one working day) of the Investigator first becoming aware.

Fatal or life-threatening SUSARs must be reported to the Ethics Committee and relevant regulatory bodies within 7 days; all other SUSARs must be reported within 15 days of knowledge if no other timelines are set out in the local drug law.

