12. STUDY SCHEDULE

12.1. Procedures at Each Visit

Visit 1: Screening/Baseline - 30-120 days from stroke onset

Patients will be informed about the study and an Informed consent will be obtained before any study-specific procedures will be carried out. Inclusion/exclusion criteria will be assessed and documented in the CRF. Patients who provide an informed consent and who meet all inclusion/exclusion criteria will be included in the study, and a randomization code will be assigned. After randomization, the medical history, vital signs, and patient demographic data as well as any concomitant medication will be measured or retrieved and recorded in the CRF. The baseline tests for all efficacy parameters (primary and secondary) will then be administered, and the results will be recorded in the CRF. Treatment with the study drug will be initiated with the first dose, and patients will receive the study drug for first 90 days of treatment.

Visit 2: 90 days from baseline

Vital signs will be taken, and changes in any of the concomitant medications will be recorded in the CRF. Any adverse events reported by the patient or noted by the investigator will be assessed and recorded in the CRF. Compliance with the study medication will be checked and recorded in the CRF. Tests for primary and secondary efficacy parameters will be administered and recorded. Patients will receive the study drug for the next 270 days of treatment.

VISIT 3: 360 days from baseline

Vital signs will be taken, and changes in any of the concomitant medications will be recorded in the CRF. Any adverse events reported by the patient or noted by the investigator will be assessed and recorded in the CRF. Compliance with the study medication will be checked and recorded in the CRF. Tests for primary and secondary efficacy parameters will be administered and recorded.

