15.2. Study Monitoring

The study coordinator will visit the investigational site at regular intervals to verify adherence to the protocol and local legal requirements and to assist the investigator in his study-related activities.

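### The safety stopping rule in section 7.3.1 covers, read literally, only serious events that are also life-threatening, and it does not point to the concurrent untreated arm as a reference

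*Protocol*

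**What the plan says.** Section 7.3.1 of the protocol gives two grounds for ending the whole study. One is slow recruitment. The other is safety, and it starts from reasonable suspicion that "any serious and life-threatening side effects occur significantly more frequently than usual in patients with the inclusion diagnosis, the study will be discontinued". The bullet does not mention the control group.

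Three other places bear on it:

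- Section 4 states that therapeutic effect and safety are assessed "in comparison to a control group of patients after stroke".
- Section 7.4 randomises 2:1 and says that "THE PATIENTS IN THE CONTROL GROUP WILL NOT RECEIVE ANY KIND OF MEDICATION OR PLACEBO". The synopsis gives 60 treated and 30 reference patients.
- Section 11.3 lists six alternative criteria for seriousness. Being life-threatening is one; another is "Requires additional inpatient hospitalization or prolongation of existing hospitalization"; another is persistent or significant disability. The note to that section confines the term life-threatening to events in which the patient was actually at risk of death at the time.

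**The concern.** The bullet is the only safety criterion in section 7.3.1 for ending the study, and it is mandatory once met, so its wording matters.

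**Scope.** Joining the two adjectives with 'and' makes the rule narrower than the protocol's own definition of a serious event. A run of hospitalisations or lasting disability in the treated arm would be serious under section 11.3, yet would not literally meet the rule.

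**Reference.** The rule asks whether events exceed what is usual in the diagnosis. The trial collects direct, concurrent evidence on that from randomised, untreated patients who met the same entry criteria, but the rule does not send the reader there. Two careful readers with different background rates in mind could reach opposite conclusions from the same count.

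At stake is how promptly and consistently an excess of harm would be recognised.

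**Working it through.** The protocol states no rate, threshold or test for this rule, so there is no figure to reproduce. Steps 1 and 2 compare the text. Steps 3 and 4 are illustrations on assumed rates.

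**1. Scope: section 7.3.1 against the six criteria of section 11.3.**

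| Criterion in 11.3 | Within the literal wording of 7.3.1? |
|---|---|
| Death | Not named, but would be covered in practice |
| Life-threatening | Yes |
| Hospitalisation, new or prolonged | Not unless also life-threatening |
| Persistent or significant disability | Not unless also life-threatening |
| Congenital anomaly | Not necessarily |
| Other medically significant event | Not necessarily |

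At least two of the six, hospitalisation and disability, need not be life-threatening. The note in 11.3 confirms that the terms differ: it tells the investigator to treat some events as serious even though they are not immediately life-threatening.

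**2. Reference: section 7.3.1 against sections 4 and 7.4.** Section 4 sets the control group as the comparator for safety, and section 7.4 supplies a randomised untreated arm. Section 7.3.1 names only the usual frequency in the diagnosis. The controls are patients with that diagnosis, so they are admitted by the wording but not named.

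**3. Why the reference matters.** Inputs: 60 treated patients (synopsis); usual rates of 2%, 5% and 10% (assumed). Suppose 7 treated patients have a qualifying event. With X ~ Binomial(60, p), the one-sided tail P(X ≥ 7) is:

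- p = 2%: 0.0002
- p = 5%: 0.030
- p = 10%: 0.39

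The same count looks extreme, borderline or unremarkable, depending on the rate the reader has in mind.

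**4. What the control arm can and cannot add.** Inputs: 60 treated and 30 controls; an event rate of 5% in both arms unless stated (assumed); X treated events and Y control events, independent binomials, fully enumerated.

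- Expected counts: 60 × 0.05 = 3 treated and 30 × 0.05 = 1.5 control.
- The treated rate exceeds the control rate when X/60 > Y/30, that is X > 2Y. The probability is 0.453.
- The treated rate is at least double when X ≥ 4Y with X ≥ 1. The probability is 0.327.
- No control events at all: 0.95^30 = 0.215.
- If the treated rate were truly 10% against 5%, a one-sided Fisher exact test at 0.05 would flag it in 6.5% of trials.

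A by-arm table is therefore useful evidence but a poor formal test, and a bare numerical lead in the treated arm means little.

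**The case against.** The strongest reply is that the rule is a judgement trigger at one centre in an open-label study. The investigator sees events in both arms, the controls already count as patients with the diagnosis, and no sensible investigator would ignore an excess of disabling or hospitalising events. The phrase may simply list two categories loosely. The product is a marketed supplement, and other protections exist: individual withdrawal (7.3.2), suspected serious reactions that "must be reported to the manufacturer within 24 hours" (11.7), and immediate-hazard changes (16.3). All of this is fair, and it keeps the point small. It does not remove it. The rule is operative text, its literal scope conflicts with 11.3, and none of those other routes compares the arms.

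Several stronger readings are tempting but not supported:

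- *The rule excludes the control arm.* It does not; it only fails to name it.
- *The lack of a rate, source or review interval is a defect.* Such detail may sit in a statistical analysis plan or monitoring document that is not shown.
- *Seriousness is defined only for drug reactions.* The lead-in "An adverse drug reaction is considered SERIOUS if it" might suggest this, but the heading and note of 11.3 also cover adverse events, and section 11.6 records all adverse events.
- *Events between visits go unrecorded.* At day 90, "Patients will receive the study drug for the next 270 days of treatment", so the visits are far apart. But section 11.6 requires recording of what is volunteered or observed during or after administration, and section 11.8 follows events throughout the study.
- *The rule has poor operating characteristics.* The protocol contains no formal test, so the figures above do not measure its performance.

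**Conclusion.** The point holds as a minor one and is best regarded as a cheap improvement. The scope half is the firmer: it follows from sections 7.3.1 and 11.3 alone and needs no assumed rate. At least two of the six seriousness criteria fall outside the literal rule. The reference half is a failure to direct the reader to evidence the trial already collects, against the comparator that section 4 sets for safety.

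The numerical illustrations rest on assumed event rates of 2% to 10%, on full arms of 60 and 30, and on one-sided tests that the protocol does not specify. They show that the choice of reference can change the conclusion and that 30 controls alone cannot settle it. No efficacy result is affected.

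**What to change.** Reword the second bullet of section 7.3.1:

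- Replace 'and' with 'or' between the two adjectives, and 'side effects' with 'adverse events'. The first restores the scope of 11.3. The second lets events be counted in untreated patients, for whom a side effect of the product has no meaning.
- Give two alternative references: a higher frequency in the treatment group than in the concurrent control group, allowing for 2:1 allocation; or a higher frequency than is usual in the diagnosis.
- Drop 'significantly', so that no formal test is implied.
- State that the judgement is made on serious adverse events in both arms, tabulated by arm from the existing CRFs.
- Keep the reasonable-suspicion threshold and the mandatory stop. Do not add a requirement that harm first be judged product-related, because that would make the rule weaker than it is now.

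The cost is a protocol amendment to one bullet and a short by-arm table for the investigator to keep. The coordinator, who already visits "to verify adherence to the protocol and local legal requirements", can check that the table is kept. No sample size, endpoint or efficacy analysis changes. The drawback is imprecision: because the treated rate leads by chance so often, the by-arm table should feed the clinical judgement of reasonable suspicion, and a numerical lead alone should not be treated as meeting it.

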7.3.2. Discontinuation Criteria Related to the Patient

Patients will be advised in the informed consent forms that they have the right to withdraw from the study at any time without prejudice, and they may be withdrawn at the investigator's discretion at any time. In the event that a patient drops out of the study or is withdrawn, the withdrawal/study termination page in the CRF should be completed. On the withdrawal page, the investigator should record the date of the withdrawal, the person who initiated withdrawal

and the reason for withdrawal. Reasonable effort should be made to contact any patient lost to follow-up during the course of the study in order to complete assessments and retrieve any outstanding data and study supplies.

Withdrawn by the Investigator due to:

- Lack of efficacy
- Adverse event
- Consent withdrawn
- Lost to follow-up
- Administrative reasons

The patient or his/her representative requested withdrawal due to:

- Adverse event (for which the investigator did not consider removal from the study)
- Perceived insufficient therapeutic effect
- Withdrawal of consent for any other reason (data recorded until withdrawal will be kept in the database if not explicitly denied by the patient).

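### Section 7.3.2 lets lack of efficacy end follow-up as well as the supplement, which in an open-label trial with untreated controls risks selective loss of day-360 data in the N-Pep-12 arm

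*Protocol*

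**What the plan says.** Section 7.3.2 provides one kind of exit, and it is from the study: "In the event that a patient drops out of the study or is withdrawn, the withdrawal/study termination page in the CRF should be completed". Withdrawal is permissive and has no stated criterion; patients are told that "they may be withdrawn at the investigator's discretion at any time". The first of the investigator's reasons is "Lack of efficacy", and one of the patient's reasons is "Perceived insufficient therapeutic effect".

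On follow-up after exit, the section says: "Reasonable effort should be made to contact any patient lost to follow-up during the course of the study in order to complete assessments". It contains no such request for patients who are withdrawn, or who withdraw, for insufficient effect. Under withdrawal of consent for any other reason it adds that "data recorded until withdrawal will be kept in the database if not explicitly denied by the patient".

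Section 5 makes the study open label. Section 7.4 allocates 2:1 and says that "THE PATIENTS IN THE CONTROL GROUP WILL NOT RECEIVE ANY KIND OF MEDICATION OR PLACEBO". Section 4 states an aim of superiority after 360 days, and the table in section 12.2 marks Visit 3 as the primary endpoint. Under section 12.1 the primary scales are also administered at day 90, when supplement for a further 270 days is handed out.

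**The concern.** A control has no study product whose effect could be judged insufficient, so the two efficacy-based reasons have no natural counterpart in that arm. The investigator knows the allocation and has the day-90 scores at the visit where the next supply is given. That is an obvious moment for either party to conclude that the supplement is not working.

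Under 7.3.2 as written, such a patient leaves the study, and nothing calls for a day-360 assessment. Missingness could then depend on both outcome and arm. If poorly recovering patients drop out of the treated arm but not the control arm, the remaining treated patients look better than the arm that was randomised.

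This belongs in the protocol. An SAP can say how missing scores are handled, but only the protocol decides whether the visit takes place, and scores never collected cannot be recovered later.

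**Working it through.** The protocol gives no dropout rate, SD, correlation, alpha or effect size, and its synopsis says no formal sample size calculation was done. There is therefore no figure to reproduce, and what follows is an illustration.

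**From the protocol:** 60 treated and 30 control patients (2:1), with primary scales at baseline, day 90 and day 360.

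**Assumed:** no true effect; outcome oriented so that higher is better and scaled to SD 1; the lowest fraction d of the treated arm at day 90 leaves; no control leaves; only completers are analysed.

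**Illustration 1: ANCOVA on baseline.** Assume a baseline/outcome correlation of 0.6 and a day-90/day-360 residual correlation of 0.6. The residual SD is √(1 − 0.6²) = 0.8. Removing the lowest fraction d of a normal variable raises the mean of the rest by φ(z_d)/(1 − d), so

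bias = 0.6 × 0.8 × φ(z_d)/(1 − d)

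- d = 10% (6 of 60): 0.1755/0.90 = 0.195; × 0.48 = 0.094 SD
- d = 20% (12 of 60): 0.280/0.80 = 0.350; × 0.48 = 0.168 SD

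Simulation (6,000 runs per scenario), with false results in favour of N-Pep-12 against a nominal 2.5%:

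| Treated arm withdrawn | Bias (SD) | False results in favour |
|---|---|---|
| 5% (3 patients) | 0.050 | 4.9% |
| 10% (6) | 0.092 | 7.7% |
| 20% (12) | 0.164 | 15.3% |

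**Illustration 2: two-sample t-test on change scores.** Let r be the day-90/day-360 correlation, so bias = r × φ(z_d)/(1 − d). Error rates come from 20,000 runs.

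| Withdrawn | Bias (SD), r = 0.3 to 0.7 | False results in favour, r = 0.5 / 0.7 |
|---|---|---|
| 0% | 0 | 2.7% / 2.5% |
| 5% | 0.03 to 0.08 | 4.3% / 5.5% |
| 10% | 0.06 to 0.14 | 6.6% / 9.6% |
| 20% | 0.11 to 0.25 | 12.1% / 20.6% |

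The two illustrations agree in direction and order of size. The 0% row also shows what happens if everyone who stops the supplement is still assessed.

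**Where the bias disappears:**

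- The worst 10% leave both arms (r = 0.5): bias 0.00 SD, 2.7% false results in favour.
- Withdrawal depends only on the day-90 score, and a missing-at-random estimate uses that score: bias 0.003 SD at 10% and 0.001 SD at 20% in the change-score set-up (r = 0.5, 5,000 runs); 0.002 and 0.001 SD in the ANCOVA set-up (4,000 runs).

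**Where it does not:** a missing-at-random analysis has nothing to condition on if the decision rests on something unrecorded. Perceived effect is a subjective judgement, no scale is scheduled between day 90 and day 360, and a patient who leaves before day 90 has no post-baseline score. The size of this case was not computed.

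**The case against.** A reader might infer that non-responders will be removed from the treated arm, that the result is therefore biased, and that no analysis could repair it. The protocol does not support that.

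- **Frequency is unknown.** The section permits withdrawal and lists reasons for it. No efficacy threshold or day-90 review triggers it. The 5% to 20% rates, the perfect selection of the worst patients and the absence of control dropout are all assumptions. This stands.
- **The reasons are not formally confined to one arm.** Controls who do poorly, or are disappointed at receiving nothing, can leave by withdrawing consent or at the investigator's discretion. That would offset the bias and, with equal loss, cancel it. This stands as a possibility, but nothing in the protocol makes the losses equal, and the two efficacy-based reasons push them apart.
- **The protocol does not specify a completers-only analysis.** The missing-data method may be in an SAP that is not among the documents. Day-90 scores should usually be in hand, and an analysis using them removes the bias in the very mechanism illustrated. This stands, and it limits the figures above to a completers analysis. It does not cover withdrawal driven by unrecorded status.
- **The study is exploratory.** The synopsis says it is not powered for pre-defined statements, and no alpha is stated for an 8% rate to breach. This lowers the severity. Section 4 nevertheless aims to show superiority, and the results are meant to inform later trials.
- **Nothing forbids assessing withdrawn patients.** True, but nothing asks for it either.

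**Conclusion.** The concern holds as a risk that the protocol creates, not as a demonstrated bias. Section 7.3.2 merges stopping the supplement with ending follow-up, and the open-label, untreated control makes the efficacy-based exits fall mainly on one arm. Day-360 data may therefore be lost in relation to outcome and arm.

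In a completers-only analysis the direction favours N-Pep-12 if controls do not leave to a similar extent. Under the ANCOVA assumptions the size is about 0.09 SD at 10% withdrawn and 0.16 SD at 20%. The chance of a false result in favour rises from 2.5% to about 8% and 15%. It is about zero with equal loss in both arms, or with withdrawal explained by recorded day-90 scores that the analysis uses. It persists if withdrawal turns on unrecorded status, such as perceived effect after day 90. Should be fixed; moderate confidence.

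**What to change.** In section 7.3.2, define two separate events: the patient stops the supplement, and the patient withdraws consent to follow-up. State that every randomised patient who stops the supplement, for whatever reason, is still invited to Visits 2 and 3 with all primary scales and is analysed in the arm to which he or she was randomised. State that only withdrawal of consent ends data collection. Record the two events separately in the CRF. Leave the reasons for which the supplement may be stopped unchanged.

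The cost is a short amendment, one CRF field, and at most two visits per patient, already in the schedule, for probably a few patients. Follow-up of these patients also spares the analysis from resting on an untestable missing-data assumption.
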